## **8.4 Informed consent**

The Principal Investigator(s) at each centre will:

- Ensure each patient is given full and adequate oral and written information about the nature, purpose, possible risk and benefit of the study
- Ensure each patient is notified that they are free to discontinue from the study at any time

- Ensure that each patient is given the opportunity to ask questions and allowed time to consider the information provided
- Ensure each patient provides signed and dated informed consent before conducting any procedure specifically for the study
- Ensure the original, signed Informed Consent Form(s) is/are stored in the Investigator's Study File
- Ensure a copy of the signed Informed Consent Form is given to the patient
- Ensure that any incentives for patients who participate in the study as well as any provisions for patients harmed as a consequence of study participation are described in the informed consent form that is approved by an Ethics Committee.

The genetic research is optional and the patient may participate in the main study without participating in the genetic component. To participate in the genetic component of the study the patient must sign and date both the consent form for the main study (non-genetic components of the study) and the genetic component of the study. Copies of both signed and dated consent forms must be given to the patient and the original filed at the study centre. The principal investigator(s) is responsible for ensuring that consent is given freely and that the patient understands that they may freely discontinue the genetic aspect of the study at any time.

## **8.5 Changes to the protocol and informed consent form**

Study procedures will not be changed without the mutual agreement of the International co-ordinating Investigator and AstraZeneca /Bristol-Myers Squibb.

If there are any substantial changes to the study protocol, then these changes will be documented in a study protocol amendment and where required in a new version of the study protocol (Revised Clinical Study Protocol).

The amendment should be approved by each Ethics Committee and if applicable, also the national regulatory authority, before implementation. Local requirements should be followed for revised protocols.

AstraZeneca will distribute any subsequent amendments and new versions of the protocol to each Principal Investigator(s). For distribution to Ethics Committee see Section [8.3](#).

If a protocol amendment requires a change to a centre's Informed Consent Form, AstraZeneca and the centre's Ethics Committee should approve the revised Informed Consent Form before the revised form is used.

If local regulations require, any administrative change will be communicated to or approved by each Ethics Committee.

The distribution of these documents to the regulatory authority will be handled according to local practice.

## **8.6 Audits and inspections**

Authorised representatives of AstraZeneca, a regulatory authority, or an Ethics Committee may perform audits or inspections at the centre, including source data verification. The purpose of an audit or inspection is to systematically and independently examine all study-related activities and documents, to determine whether these activities were conducted, and data were recorded, analysed, and accurately reported according to the protocol, Good Clinical Practice (GCP), guidelines of the International Conference on Harmonisation (ICH), and any applicable regulatory requirements. The investigator will contact AstraZeneca immediately if contacted by a regulatory agency about an inspection at the centre.

## **9. STUDY MANAGEMENT BY ASTRAZENECA**

### **9.1 Pre-study activities**

Before the first patient is entered into the study, it is necessary for a representative of AstraZeneca to visit the investigational study site to:

- Determine the adequacy of the facilities
- Determine availability of appropriate patients for the study
- Discuss with the investigator(s) (and other personnel involved with the study) their responsibilities with regard to protocol adherence, and the responsibilities of AstraZeneca or its representatives. This will be documented in a Clinical Study Agreement between AstraZeneca and the investigator.

### **9.2 Training of study site personnel**

Before the first patient is entered into the study, an AstraZeneca representative will review and discuss the requirements of the Clinical Study Protocol and related documents with the investigational staff and also train them in any study specific procedures and WBDC system utilised.

The Principal Investigator will ensure that appropriate training relevant to the study is given to all of these staff, and that any new information relevant to the performance of this study is forwarded to the staff involved.

The Principal Investigator will maintain a record of all individuals involved in the study (medical, nursing and other staff).

Prior to the study start regional meetings will be held with all investigators and/or other staff involved from each study centre and AstraZeneca representatives. During the meeting,

participants will have an opportunity to discuss the procedures associated with the study, the requirements for collection of blood samples and the genetics part in accordance with [Appendix D](#). The importance of the informed consent process will be made clear.

### **9.3 Monitoring of the study**

During the study, an AstraZeneca representative will have regular contacts with the study site, including visits to:

- Provide information and support to the investigator(s)
- Confirm that facilities remain acceptable
- Confirm that the investigational team is adhering to the protocol, that data are being accurately and timely recorded in the eCRFs, that biological samples are handled in accordance with the Laboratory Manual and that investigational product accountability checks are being performed
- Perform source data verification (a comparison of the data in the eCRFs with the patient's medical records at the hospital or practice, and other records relevant to the study) including verification of informed consent of participating patients. This will require direct access to all original records for each patient (eg, clinic charts)
- Ensure withdrawal of informed consent to the use of the patient's biological samples is reported and biological samples are identified and disposed of/destroyed accordingly, and the action is documented, and reported to the patient.

The AstraZeneca representative will be available between visits if the investigator(s) or other staff at the centre needs information and advice about the study conduct.

#### **9.3.1 Source data**

Refer to the Clinical Study Agreement for location of source data.

#### **9.3.2 Direct access to source data in Japan (Not Applicable)**

### **9.4 Study agreements**

The Principal Investigator at each/the centre should comply with all the terms, conditions, and obligations of the Clinical Study Agreement, or equivalent, for this study. In the event of any inconsistency between this Clinical Study Protocol and the Clinical Study Agreement, the terms of Clinical Study Protocol shall prevail with respect to the conduct of the study and the treatment of patients and in all other respects, not relating to study conduct or treatment of patients, the terms of the Clinical Study Agreement shall prevail.

Agreements between AstraZeneca and the Principal Investigator should be in place before any study-related procedures can take place, or patients are enrolled.

#### **9.4.1 Archiving of study documents**

The Investigator follows the principles outlined in the Clinical Study Agreement (CSA).

#### **9.5 Study timetable and end of study**

The end of the study is defined as ‘the last visit of the last patient undergoing the study’.

The study is expected to start in Q1 2010 and to end by Q1 2013.

The study may be terminated at individual centres if the study procedures are not being performed according to GCP, or if recruitment is slow. AstraZeneca may also terminate the entire study prematurely if concerns for safety arise within this study or in any other study with dapagliflozin.

### **10. DATA MANAGEMENT**

Data management will be performed by Data Management Centre staff.

Data will be entered in the Web Based Data Capture (WBDC) system at the study site. Trained study personnel will be responsible for entering data on the observations, tests and assessments specified in the protocol into the WBDC system and according to the eCRF Instructions. The eCRF Instructions will also guide the study site in performing data entry. Data entered in the WBDC system will be immediately saved to a central database and changes tracked to provide an audit trail. The data will then be Source Data Verified (SDV), reviewed/ queried and updated as needed. Principal Investigator is responsible for signing the eCRF and this can be delegated to a trained Investigator. The eCRF is signed electronically as per the eCRF instructions.

Data queries will be raised for inconsistent, impossible or missing data. All entries to the study database will be available in an audit trail. Quality assurance procedures will be applied to each stage of data handling to ensure that all data are reliable and have been processed correctly.

The data will be frozen and then locked to prevent further editing. When all data have been coded, validated, signed and locked, clean file will be declared. Any treatment revealing data may thereafter be added and the final database will be locked. Copy of the eCRF will be archived at the study site when the study has been locked.

The study Data Management Plan will describe in greater detail the methods used to collect, check, and process clinical data. It will also clarify the roles and responsibilities of the various functions and personnel involved in the data management process. Prior to breaking the treatment codes, all decisions on the evaluability of the data from each individual patient must have been made and documented. Following database lock, required amendments to the database due to critical errors will only be allowed with the appropriate supporting

documentation. Non-critical errors will not result in amendments to the database but will be captured via the appropriate documentation.

### **Management of external data**

Data Management determines the format of the data to be received from external vendors and coordinates the flow of data to an external environment or clinical database (if applicable). Data Management will ensure that the data collection tool (eg, IWRS etc) will be tested / validated as needed. External data reconciliation will be done with the clinical database as applicable.

### **Dictionary coding**

Adverse events and medical/surgical history will be classified according to the terminology of the latest version the Medical Dictionary for Regulatory Activities (MedDRA). Medications will be classified according to the Bristol-Myers Squibb Drug Dictionary. All coding will be performed by the coding team at Bristol-Myers Squibb.

### **Management of genotype data**

Genotype data generated in this study will be stored in the Bristol-Myers Squibb and/or AstraZeneca database, or other appropriate secure system, separate from the database used for the main study. Some or all of the clinical datasets from the main study may be duplicated within the Bristol Myers Squibb and/or AstraZeneca secure databases to facilitate exploratory genetic analyses.

Any results from this genetic research will be reported separately from the clinical study report for the main study.

### **Data associated with biological samples**

Data associated with biological samples will be transferred to laboratories internal or external to AstraZeneca and Bristol-Myers Squibb.

## **11. EVALUATION AND CALCULATION OF VARIABLES BY ASTRAZENECA**

### **11.1 Calculation or derivation of efficacy variable(s)**

Please see Section 6.3.1 for a description of specific efficacy variables derived from single laboratory measures.

#### **11.1.1 Change and percent change from baseline**

Change from baseline will be calculated as absolute difference between the value measured at or derived for a specific time point after baseline minus baseline value. Baseline is defined as the day to first randomised dose, and the baseline value is the last assessment on or prior to the day of first randomised dose.

Percent change from baseline will be computed as  $100 \times (\text{value measured at or derived for a specific time point after baseline} - \text{baseline value}) / \text{baseline value}$ .

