### **3.1.1.3 Placebo lead-in period (Visits 2 and 3, week –4 to week 0)**

At the beginning of the placebo lead-in period (Visit 2, week –4) patients will undergo repeated assessment of all inclusion/exclusion criteria. At Visit 2, eligible patients will be given placebo in a single-blind fashion (blind to the patient only).

A glucometer and patient diary will be provided to patients who will be instructed to monitor their fasting plasma glucose (FPG) at least every second day and to enter the results into the patient diary. Investigators may instruct patients to monitor their FPG more often, according to their local treatment guidelines or clinical judgement. FPG monitoring procedures and assessment of hypoglycaemic events are described in Section 6.4.9.1.

Anti-diabetic drugs except insulin cannot be changed. The dose of insulin can be changed by no more than a ten percent (10%) difference in the total daily insulin use (example: when 40 U of insulin is the daily dose, the allowed change is not more than 10%, or 4 U). The dose of anti-hypertensive drugs can be changed. Anti-platelet drugs and lipid lowering drugs can be added, withdrawn or dose changed.

Starting from Visit 2, throughout the entire duration of the study, patients treated with insulin will be asked to record their daily dose of insulin in their diary.

At **Visit 3** (week -2), patients will attend to assess the glycaemic control through the diary (FPG) and a blood sample for HbA1c. Also those patients who are on insulin therapy will be reminded to record their daily insulin dose into their diary. Concomitant medications and changes will be recorded. Allowed changes in background therapy are shown in [Table 2](#). Patients will get dietary and lifestyle advice.

No changes are allowed in anti-diabetic drugs, anti-hypertensive drugs, anti-platelet drugs and lipid lowering drugs. The dose of insulin can be changed.

HbA1c measured from the sample taken at Visit 3 will be used for assessment of eligibility at Randomisation Visit (Visit 4).

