#### **6.4.8 Vital signs**

##### **6.4.8.1 Pulse and blood pressure**

One pulse measurement will be taken after the patient has been sitting and resting for at least 5 minutes and before blood samples are taken. The pulse measurement will be followed by three blood pressure (BP) measurements separated by 2 minutes each. All three BP readings should be recorded. At Visit 1 the seated BP will be recorded three times in both the left and the right arms. All three measurements should be made in one arm before transferring the cuff to the other arm. The arm with the highest mean seated BP readings will be the one used for all subsequent readings throughout the study. BP readings should be taken while the patient is in a comfortable seated position with the arm supported at the level of the heart. All readings should be recorded. Ideally, blood pressure should be measured with the same machine, at the same time of day, and by the same personnel at each visit. A standard mercury sphygmomanometer with a standardised cuff adapted to the size of the patient's arm is recommended. Oscillometric devices (such as Dynamap) may be used at sites where:

- a mercury sphygmomanometer is not available, or

- a mercury sphygmomanometer is available, but site staff is not practiced in its use
- use of mercury devices is restricted by local law.

New oscillometric devices must be recalibrated when the certificate of calibration provided by vendor expires. Thereafter the devices must be calibrated with a frequency according to local regulation but at least annually and calibration must be documented. Aneroid devices should not be used.

At each visit, three blood pressure (BP) measurements separated by 2 minutes each will be done. All three BP readings should be recorded and entered in eCRF.

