### **11.2.2 Other safety variables**

The safety evaluations will include analyses of AEs, laboratory parameters, ECG, vital signs (pulse and BP), orthostatic BP, hypoglycaemic events, calculated creatinine clearance, estimated GFR (eGFR) and physical examination. The analysis of safety will be based on the safety analysis set. Safety data gained during the 24-week double-blind treatment period, the

28-week and the 52-week extension periods and the 3-week safety follow-up period will be evaluated. Safety variables will be summarized descriptively. CV events will be analyzed in conjunction with CV events observed in other Phase II and Phase III dapagliflozin studies and the combined results will be reported elsewhere.

The Cockcroft-Gault formula will be used to calculate creatinine clearance.

Males:

$$\text{Creatinine clearance (mL/min)} = \frac{\text{Weight (kg)} \times (140 - \text{Age})}{72 \times \text{serum creatinine (mg/dL)}}$$

Females:

$$\text{Creatinine clearance (mL/min)} = \frac{\text{Weight (kg)} \times (140 - \text{Age})}{72 \times \text{serum creatinine (mg/dL)}} \times 0.85$$

The MDRD equation will be used to calculate eGFR.

The mean of the 3 BP measurements will be computed by AstraZeneca for each position for each patient at each visit.

BMI will be computed by AstraZeneca ( $\text{BMI} = \text{weight} / \text{height}^2$ , where weight is measured in kg, and height in metres).

Patients reporting at least one episode of hypoglycaemia between baseline and week 24 will be tabulated using counts and proportions.

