The LOCF approach means that for all changes (or percent changes) from baseline to a specific time point post-baseline, analyses will be based on measurements available at that time point or the last post-baseline measurement prior to the time point, if no measurement is available at that time point. This LOCF approach will be used for all variables regardless of rescue medication. In addition, unless otherwise specified, if a patient initiates rescue medication (including an increase in dose of baseline medication), the last value taken on or before the first rescue dose will be used for analysis. This last rule will apply only to glycaemic and blood pressure variables (ie, rescue for glycaemic control applied only to analysis of HbA1c and FPG changes and responder derivations, whereas rescue for blood pressure control only applied to analysis of SBP and DBP changes and responder derivations).

The first primary efficacy variable, change in HbA1c from baseline to week 24, will be analyzed by an analysis of covariance (ANCOVA) model. When assessing the results overall, the model will include terms for treatment group, age-by-insulin use-by-time from most recent qualifying CV event group (8 levels), and baseline covariate. To help characterize the treatment effect, a secondary test for interaction between treatment group and age strata will be performed at the 0.10 level of significance; however, the results of this test will not alter the conclusion from the previously specified model since the effect of dapagliflozin versus placebo will be examined for each age stratum separately. When assessing the results within each age stratum, the ANCOVA model will include terms for treatment group, insulin use-by-time from most recent qualifying CV event group (4 levels), and baseline covariate. The ANCOVA model will be used to derive a least squares estimate of the treatment difference with 95% confidence interval and corresponding two-sided p-value. Further, two-sided 95% confidence intervals for the mean change within each treatment group will be calculated. The same method will be applied for analyzing other continuous efficacy variables. For variables analyzed as percent change from baseline, the ANCOVA model will apply to logarithm-transformed data and resulting least-squares means and confidence intervals back-transformed to provide estimates in the original scale.

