## **2.4 Visit 3 (week -2)**

Visit 3 will occur 3 weeks after Visit 1.

The following procedures should be done in the order shown:

- Measure blood pressure and pulse
- Draw a blood sample for HbA1c (to be used for evaluation on inclusion criterion at Randomisation) and send to the central laboratory
- Draw a blood sample and send to the central laboratory
- Do a urine pregnancy test (only applicable to women of childbearing potential)
- After blood pressure measurement, and blood and urine sampling, patient should take investigational product along with other medications. Patient should have a breakfast within 30 minutes after taking medications.
- Review patient's diary for glucometer values/hypoglycaemic events and insulin dose (if applicable) and dispense new diary
- Instruct patient that the insulin dose needs to be recorded daily and that the dose will be reduced by 25% at Visit 4
- Collect and document AEs and SAEs and fill in event forms when applicable

- Document concomitant medications; for anti-hyperglycaemic, anti-hypertensive, lipid lowering and anti-platelet medications daily dose should be recorded in eCRF
- Give diet and lifestyle advice
- Schedule Visit 4 five weeks after Visit 1, ask the patient to be fasting and give instructions what concomitant medications are allowed to take in the morning of the next visit
- Complete eCRF within 72 hours.

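### Optional precision gain: the SBP key secondaries adjust for one pre-dose visit, although the Visit 3 seated mean is also collected and could serve as a second covariate

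*Supplement*

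**What the plan says.** - **Baseline.** Section 11.1.1: "the baseline value is the last assessment on or prior to the day of first randomised dose". Blood pressure is measured at Visit 4 before the first dose, so Visit 4 supplies the SBP baseline.
- **What one visit's value is.** Section 6.4.8.1: "At each visit, three blood pressure (BP) measurements separated by 2 minutes each will be done". Section 11.2.2: "The mean of the 3 BP measurements will be computed by AstraZeneca for each position for each patient at each visit". The baseline is therefore the mean of three seated readings at one visit.
- **Model.** Section 12.2.1 specifies, for the overall population, "terms for treatment group, age-by-insulin use-by-time from most recent qualifying CV event group (8 levels), and baseline covariate". Within an age stratum it specifies treatment group, "insulin use-by-time from most recent qualifying CV event group (4 levels), and baseline covariate". It then says: "The same method will be applied for analyzing other continuous efficacy variables". SBP change at weeks 8 and 24 falls under that sentence.
- **Visit 3.** Appendix E Section 2.4 (week -2) begins with "Measure blood pressure and pulse". Section 3.1.1.3 says of this visit: "No changes are allowed in anti-diabetic drugs, anti-hypertensive drugs, anti-platelet drugs and lipid lowering drugs". Table 2 agrees: the last permitted anti-hypertensive change is a dose change at Visit 2 (week -4).
- **Testing order.** Section 12.2.1 puts SBP at week 8 first and SBP at week 24 third among the key secondaries. They are tested in fixed order, separately in the overall population and each age stratum. A stream runs at 0.05 or 0.025 (two-sided), depending on the primaries, and stops at its first failure.

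**The concern.** Averaging three readings a few minutes apart reduces within-visit error but leaves variation between visits, which one baseline visit cannot separate from the patient's usual pressure. The Visit 3 mean carries further information on that usual level. It precedes randomisation and was taken on the same anti-hypertensive regimen as Visit 4, and no section uses it in the efficacy model.

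What is at stake is precision. If week-8 SBP fails in a population, percent weight change, week-24 SBP and the 5% weight-loss responder test get no confirmatory inference there. Section 12.3 justifies the sample size on the two primary endpoints only and states no power for SBP.

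**Working it through.** **1. The plan's own figure.** There is no SBP calculation to reproduce, but the sample size supplies n. For 25% versus 10% at two-sided 0.0125 with 90% power (pooled chi-square):

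n = [2.498·√(2·0.175·0.825) + 1.282·√(0.25·0.75 + 0.10·0.90)]² / 0.15² = 180.9, so 181 per arm.

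Then 362/0.963 = 376 and 376/0.40 = 940, all as in Section 12.3. Evaluable patients per arm are 181 in a stratum at the 40% floor, 470·0.963/2 ≈ 226 in a stratum of the planned size, and 940·0.963/2 ≈ 452 overall.

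**2. Formula.** Let r4 and r3 be the correlations of the Visit 4 and Visit 3 means with the outcome visit, and r34 their correlation with each other. With Visit 4 alone the residual variance is proportional to 1 − r4². Adding Visit 3 cuts it by the fraction

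cut = (r3 − r4·r34)² / [(1 − r34²)(1 − r4²)].

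The SD cancels. With all three correlations equal to ρ this becomes ρ²/(1+ρ)².

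**3. Equal correlation (assumed ρ).**

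| ρ | Visit 4 only, 1−ρ² | Both, 1−2ρ²/(1+ρ) | Cut |
|---|---|---|---|
| 0.3 | 0.910 | 0.862 | 5.3% |
| 0.5 | 0.750 | 0.667 | 11.1% |
| 0.6 | 0.640 | 0.550 | 14.1% |
| 0.7 | 0.510 | 0.424 | 17.0% |
| 0.8 | 0.360 | 0.289 | 19.8% |

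For ρ of 0.5–0.7 the cut is worth 12.5–20.4% more patients on this endpoint. Simulating the <160 mmHg rule at Visit 4 gave 11.2% and 16.8% at ρ = 0.5 and 0.7, so truncation does not change the result.

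**4. Correlation decaying with time**, r(t) = ρ·exp(−t/τ), with lags of 2, 8 and 10 weeks for week 8 and 2, 24 and 26 weeks for week 24 (ρ and τ assumed).

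| ρ | τ (weeks) | Cut, week 8 | Cut, week 24 |
|---|---|---|---|
| 0.5 | 100 | 8.6% | 5.8% |
| 0.6 | 100 | 10.4% | 6.7% |
| 0.7 | 100 | 11.7% | 7.1% |
| 0.5 | 52 | 6.8% | 3.3% |
| 0.6 | 52 | 8.0% | 3.7% |
| 0.7 | 52 | 8.6% | 3.7% |

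Faster decay (τ = 26) gives 4–5% at week 8 and about 1% at week 24.

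**5. Visit 3 clearly less predictive than Visit 4.**
- r4 = 0.6, r3 = 0.5, r34 = 0.7: (0.5 − 0.42)²/(0.51·0.64) = 2.0%.
- The same with r34 = 0.6: (0.5 − 0.36)²/(0.64·0.64) = 4.8%.
- r4 = 0.7, r3 = 0.6, r34 = 0.7: (0.6 − 0.49)²/(0.51·0.51) = 4.7%.

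**6. What it buys in power.** Assume a 3 mmHg effect and a pressure SD of 13–15. Power = Φ(3/SE − z), with SE = SD·√[2(1−ρ²)(1−cut)/n]. The ranges run from SD 15 with ρ = 0.5 to SD 13 with ρ = 0.7, using the favourable cuts of step 3.

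| Evaluable per arm | α | Visit 4 only | Both visits |
|---|---|---|---|
| 181 (smallest stratum) | 0.05 | 59–87% | 64–92% |
| 181 | 0.025 | 48–80% | 54–87% |
| 226 (planned stratum) | 0.05 | 69–93% | 74–96% |
| 226 | 0.025 | 58–88% | 64–94% |
| 452 (overall) | 0.05 | 93–99.8% | 96–99.96% |
| 452 | 0.025 | 89–99.6% | 93–99.9% |

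Independently of effect and SD, a week-8 test with 80% power gains about 1 point from a 2% cut, 3–5 points from 7–12%, and 4–7 points from 11–17%.

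**The case against.** The strongest reply is that nothing here is wrong. ANCOVA with one baseline covariate is standard, valid and controls Type I error, and the protocol claims no power for SBP that could be missed. That stands, and it makes this an optional improvement.

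The second reply is that the larger figures need Visit 3 to predict week 8 as well as Visit 4 does. Table 2 gives a reason for doubt: drugs may be added or withdrawn at Visit 1 and doses changed at Visit 2, so Visit 3 comes only two to three weeks after permitted changes. An unchanged regimen need not mean settled pressure. This also stands, and it is why the range reaches down to about 2%.

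Third, the 181-per-arm illustration is the least favourable case. With a stratum of the planned size power is higher, and in the overall population there is little left to gain.

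Fourth, the SAP is not shown and may add the covariate. That cannot be excluded. But Section 12.2.1 lists the model terms itself; it defers subgroups, pooling of countries and EQ-5D methods to the SAP, and does not defer this.

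A reader might infer that the model rests on a single noisy reading. It does not: Sections 6.4.8.1 and 11.2.2 make it a mean of three. A reader might also think the <160 mmHg limit at randomisation aggravates the loss; the simulation shows that it does not.

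**Conclusion.** The point holds as a free gain in precision. The Visit 3 seated mean is available, precedes randomisation, follows the last permitted anti-hypertensive change and is unused. Adding it leaves the estimand and Type I error as they are.

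The size depends on correlations that the documents do not give. At week 8 a fair statement is a cut in residual variance of roughly 2–17%, with 7–12% under slow decay. At week 24 it is about 3–7% under the same decay. The practical value lies mainly in the two age-stratum streams, where week-8 SBP is the opening test.

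Two stronger readings are tempting. One is that 11–17% is the gain to expect; it is the result only under equal between-visit correlation of 0.5–0.7. The other is that the SBP analysis is biased or the sequence underpowered by error. The documents support neither: the analysis is unbiased, and no SBP effect, SD or power is stated against which to judge it.

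**What to change.** In Section 12.2.1 (and the SAP), before the 24-week unblinding, state that the ANCOVA for change in seated SBP and DBP includes the Visit 3 mean seated pressure (systolic or diastolic, to match) as a second covariate beside the Visit 4 baseline. Keep change from Visit 4 as the endpoint and all other terms as they are. Replace a missing Visit 3 value with the Visit 4 value, so that nobody is dropped. Stay with the planned ANCOVA; no other model is needed.

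The cost is one sentence and one degree of freedom, with no new visits, data or patients. It must be fixed in advance, because choosing covariates after seeing treatment results would undo the benefit.
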